In details, a composite outcome measure will be defined as primary endpoint of the study according to patient's age, as follows:

- in patients < 10 years of age treatment success will be defined only in terms of serum ferritin level (criterion A);
- in patients ≥ 10 years of age treatment success will be defined in terms of both serum ferritin level and cardiac MRI T2* (criteria A and B).

In patients ≥ 10 years of age who would require sedation for the MRI scan, treatment success will be defined only in terms of serum ferritin level (criterion A). Details on the choice of the composite outcome are in **Section 11.1**.

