4.3.1 Definition of successful chelation

The following criteria will be used to identify a treatment success:

- Criterion A - Serum Ferritin Levels:** success for patients with baseline serum ferritin levels of 2500 ng/mL or more will be defined as a 20% reduction or more after 1 year treatment. Success for patients with baseline serum ferritin levels less than 2500 ng/mL will be defined as any decrease in serum ferritin, or an increase in serum ferritin, if that increase is less than or equal to 15% of the baseline level, as long as the increase does not result in a serum ferritin above 2500 ng/mL within 12 months despite continual transfusional therapy.
- Criterion B - MRI T2* Cardiac Iron Concentration:** success for patients with baseline values of 20 ms or more will be defined as any increase in T2* or, if there is a decrease, the decline is not more than 10% after 1 year, as long as this does not result in a value below 20 ms. Success in patients with a baseline less than 20 ms will be defined as an increase in T2* of 10% or more despite transfusional therapy.

Table 1 summarises the applied criteria.

Table 1. Definition of treatment success

Baseline ferritin \geq 2500 ng/mL	Reduction of 20% or more after 1 year treatment
Baseline ferritin $<$ 2500 ng/mL	
 any decrease increase \leq 15% as long as the increase doesn't result in ferritin $>$ 2500 ng/ml after 1 year treatment
Baseline MRI T2* $<$ 20 ms	
 Increase of 10% or more after 1 year treatment
Baseline MRI T2* \geq 20 ms	
 any increase decrease \leq 10% after 1 year treatment as long as the decrease does not result in MRI T2* value $<$ 20 ms

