11. STATISTICAL CONSIDERATIONS

11.1 General Design Issues

This is a multicenter trial primarily aimed at demonstrating the non-inferiority of DFP to DFX in terms of percentage of successfully chelated patients after one-year treatment.

A non-inferiority study is considered the appropriate design for this trial for the reasons outlined in **Section 4** and further detailed below. No studies directly comparing DFP and DFX are available, however extensive literature is published comparing the efficacy of both IMPs with DFO. In particular, DFP results as efficacious as DFO in reducing serum ferritin levels in several studies in adults and children (Olivieri et al, 1990; Olivieri & Brittenham, 1998; Aydinok et al, 1999, 2007; Maggio et al, 2002; Maggio et al, 2010; Gomber et al, 2004; Galanello et al, 2006; Ha et al, 2006; Pennell et al, 2006; Cappellini MD et al. 2006; Tanner et al, 2008; El-Beshlawy et al, 2008). Concerning DFX, a recent Cochrane review showed that an efficacy comparable to DFO can be achieved depending on the ratio of doses of DFO and DFX being compared; similar or superior efficacy for ferritin and LIC could only be achieved in the highly iron-overloaded subgroup treated at mean doses between 28 and 52 mg/day (Meerpohl JJ et al, 2012).

The analysis is based on a success criterion defined in terms of serum ferritin and cardiac iron load (see **Section 4.3**) applied to paediatric population affected by hereditary haemoglobinopathies requiring chronic transfusion and chelation.

A composite outcome measure including ferritin and cardiac MRI T2* is considered an updated and multi-factorial clinical evaluation of iron overload in this experimental population, as further detailed in **Section 4**. As cardiac MRI T2* evaluation is generally uninformative and burdensome under 10 years of age because of the need of sedation, the outcome measure has been tailored to the age of the patient at a threshold of 10 years.

A successfully chelated patient in this trial is hence defined as follows:

- a patient satisfying the criterion A in **Section 4.3.1** based on ferritin levels if the patient is < 10 years of age;
- a patient satisfying criterion A and criterion B in **Section 4.3.1** based on both ferritin levels and cardiac MRI T2* in patients \geq 10 years of age.

For ethical reasons, the sole criterion A will be applied also to patients \geq 10 years of age who would require sedation during the MRI assessment.

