The choice of this composite endpoint allows the feasibility of the trial in the entire paediatric population and provides an up to date approach to the evaluation of the global iron accumulation in paediatric transfusion-dependent patients. In addition the use of a composite endpoint (rather than an alternative one) allows avoiding multiplicity while adequately characterising (total body iron load and in the heart) the beneficial effect of treatments.

Each component of the composite endpoint will be considered for secondary analyses with the intent to clarify the interpretation of the composite. For such analyses no adjustment for multiplicity will be foreseen (see **Section 11.2**).

Based on the above defined composite endpoint, non inferiority is established if the lower limit of two sided 95% confidence interval of the difference in success rate is above - 12.5%. The choice of this margin is based on clinical considerations starting from the available evidences for the effects of DFP and DFX on ferritin levels and cardiac iron load.

In details, the percentage of expected success for DFX and DFP measured as change from baseline to 1 year treatment is summarised in the following **Table 6**:

Table 6: Success rates for DFP and DFX

Serum ferritin levels	76% (95%CI: 63.6-88.5) DFP mean dose 66.4 mg/kg/day (Addis A et al, 1999) Paediatric population included in the meta-analysis but not analysed separately.	57% (95%CI: 50.7-63.3) DFX used at 20-30 mg/kg/day (Taher A et al, 2009) 75 adult and 162 paediatric patients
Cardiac MRI T2*	66% Higher percentage in splenectomised patients (Pennell DJ et al, 2006) 29 adults	69.5% in patients with moderate-to-mild baseline cardiac iron load (≥ 10 to <20 ms) DFX mean dose 33.1 \pm 3.7 mg/kg/day (Pennell DJ et al, 2010) 72 adult and 29 paediatric patients

Pooling together these findings, the expected percentage of success in the composite endpoint is assumed to be equal to 65% and 67.5% for DFX and DFP, respectively. The non inferiority margin of 12.5% has been considered to be a good estimate of an achievable lower bound of the true difference between the DFP and DFX.

Other secondary objectives include the evaluation of treatment efficacy in terms of liver iron concentration, the assessment of treatment safety and tolerability profiles, healthcare resources utilisation and patient global assessment and the analysis of the relationship of the demographic covariates and the disposition of DFP.

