11.12 Sample Size and power considerations

Primary efficacy objective

Assuming type I and type II errors of 0.025 and 0.20, respectively, and a one-sided test, and under the assumptions that the expected proportion of subjects declared treatment successes in the DFX arm is 65%, and the expected proportion of subjects declared treatment successes in the DFP arm is 67.5% a sample size of 310 subjects, randomized in a 1:1 ratio to DFP or DPX will yield 80% power to demonstrate non-inferiority of DFP versus DFX. Taking into account a possible dropout rate of about 20% a total enrolment of 388 patients aged from 1 month to less than 18 years are expected to be included in the trial.

Secondary efficacy objective

Sample size requirements for the secondary efficacy objectives (non-inferiority in terms of ferritin levels and cardiac MRI T2*) are provided in the following.

Based on published literature, testing for non-inferiority is appropriate also when comparing DFP to DFX efficacy in terms of serum ferritin levels. In this case, considering a hypothesis testing on the continuous measure, a non inferiority margin of 400 ng/ml is considered a reliable estimate of the true allowed maximum difference between the IMPs in order to assume DFP to be non-inferior to DFX in controlling iron overload in patients affected by hereditary haemoglobinopathies. The standard deviation of the differences is available by pooling findings from paediatric studies conducted in Europe and outside (El Alfay M et al., 2010), and a reliable and conservative estimate can be 1000 ng/mL.

On these assumptions, 310 evaluable patients are sufficient to provide at least 90% power to demonstrate non inferiority of DFP to DFX, assuming a type I error of 0.025 and a one-sided test.

When considering efficacy in terms of cardiac MRI T2*, less reliable estimates of treatment efficacy are available, especially in the paediatric population. However, there are no reasons for not assuming at least a non inferiority of DFP to DFX, considering also the known beneficial effects of DFP at the cardiac level. Based on the limited published figures of cardiac MRI T2* in the paediatric population and taking into account adult data, some plausible scenarios of sample sizes and related powers are provided in the following **Table 7**, assuming a type I error of 0.025 and a one-sided test. Detailed power curves will be provided in the statistical plan.

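### Section 11.1 attributes the 65% DFX composite rate to pooling Table 6, but under the endpoint rule Table 6's 57% ferritin rate for DFX allows no composite above 57%

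*Combined protocol and SAP*

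**What the plan says.** Section 4.3 sets the endpoint by age. Under 10 years, success is ferritin alone (criterion A). From 10 years, "treatment success will be defined in terms of both serum ferritin level and cardiac MRI T2* (criteria A and B"). Section 11.1 repeats this and adds that "the sole criterion A will be applied also to patients" aged 10 or over who would need sedation for the scan. Criterion A thus applies to everyone, and criterion B is only ever an additional requirement.

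Section 11.1 presents Table 6 as the expected result: "the percentage of expected success for DFX and DFP measured as change from baseline to 1 year treatment is summarised" there. For DFX the table gives ferritin success of "57% (95%CI: 50.7-63.3") and cardiac success of "69.5% in patients with moderate-to-mild baseline cardiac iron load". For DFP it gives 76% (63.6 to 88.5) and 66%. The next sentence reads "Pooling together these findings, the expected percentage of success in the composite endpoint is assumed to be equal to 65% and 67.5" (per cent, DFX then DFP).

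Section 11.12 carries these rates into the sample size, where "the expected proportion of subjects declared treatment successes in the DFX arm is 65"% and the DFP proportion is 67.5%. This gives 310 evaluable patients for 80% power, and 388 enrolled after about 20% dropout. No pooling formula, weights, scanned share or dependence between the two criteria is stated.

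**The concern.** A patient who meets both A and B has met A. Within one population and one definition of success, the share meeting the composite cannot be larger than the share meeting A. Table 6 puts the DFX ferritin rate at 57%, yet the composite said to be pooled from that table is 65%.

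The DFX rate is one of the two inputs to the primary sample size. If its stated source cannot produce it, a reader cannot tell whether 65% is a literature figure or a judgement about how DFX will perform under criterion A. Nor can the reader see how far the 80% power depends on that judgement.

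**Working it through.** **Inputs.** Table 6: DFX ferritin 57% and cardiac 69.5%; DFP ferritin 76% and cardiac 66%. Sections 11.6 and 11.12: margin 12.5 points, one-sided 0.025, unpooled variance, 155 evaluable per arm. The scanned share f is not given, so it is an assumption here. The 60-70% in sections 11.6 and 11.12 is a condition for the secondary T2* test, not a forecast, and is used only as an illustration.

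**1. The plan's own figure.** n per arm = (1.96 + 0.8416)² × (0.675 × 0.325 + 0.65 × 0.35) / 0.15² = 155.9, against 155 stated. With power = Φ[(0.125 + p_DFP − p_DFX)/SE − 1.96] and SE = √[(p_DFP(1 − p_DFP) + p_DFX(1 − p_DFX))/155], power at 155 per arm is 79.8%. Also, 310/0.80 = 387.5, rounded up to 388. The calculation reproduces from its inputs.

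**2. The limit.** The endpoint rule is p = (1 − f) × pA + f × P(A and B). Since P(A and B) ≤ pA, p ≤ pA for any f, any T2* rate and any dependence. With pA = 57%, the DFX composite is at most 57%, or 63.3% at the upper confidence limit. The table's interval reproduces with 75 + 162 = 237 patients: SE = √(0.57 × 0.43/237) = 0.0322. So 65% is 0.08/0.0322 = 2.5 standard errors above 57%. The DFP rate of 67.5% does not meet this obstacle, because it is below 76%.

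**3. Where 65% could come from.** It lies between 57% and 69.5%, so within Table 6 only an average of the rows reaches it. Equal weights give 63.25% (DFX) and 71.0% (DFP). Weighting DFX by the table's patient numbers gives (57 × 237 + 69.5 × 101)/338 = 60.7%. To reach 65%, the ferritin row needs weight (69.5 − 65)/(69.5 − 57) = 0.36; DFP at 67.5% needs (67.5 − 66)/(76 − 66) = 0.15. This is supporting evidence only, since weights could differ by arm.

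**4. Composites under the endpoint rule, from Table 6 point estimates.**

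| f | A-B dependence | DFX | DFP |
|---|---|---|---|
| 0.6 | independent | 46.6% | 60.5% |
| 0.6 | maximum overlap | 57.0% | 70.0% |
| 0.7 | independent | 44.8% | 57.9% |
| 0.7 | maximum overlap | 57.0% | 69.0% |

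The independent DFX figures apply 69.5%, reported for baseline T2* of 10 to <20 ms, to all scanned patients. They are probably low. The 57% limit does not use that rate.

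**5. Power at 155 per arm.**

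| DFX v DFP | Basis | Power |
|---|---|---|
| 65% v 67.5% | as planned | 79.8% |
| 63.3% v 65.8% | upper limit, +2.5 points kept | 78.9% |
| 57% v 59.5% | limit, +2.5 points kept | 76.4% |
| 57% v 57% | limit, no difference | 60.4% |
| 57.0% v 57.9% | Table 6, f = 0.7, DFX maximum overlap, DFP independent | about 67% |

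With Table 6 point estimates in both arms and the same non-negative A-B correlation in each, power is 99.3% to 99.7% at f = 0.6 to 0.7. Its minimum over all f is 96.9% (f = 1, 57% v 66%, rounded).

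**The case against.** The strongest reply is that 57% need not be the trial's criterion A rate. Table 6 does not say how its DFX ferritin source defined success. Below 2500 ng/mL, criterion A also credits "an increase in serum ferritin, if that increase is less than or equal to 15% of the baseline level", provided the result stays at or below 2500. The 57% comes from 75 adults and 162 children at 20-30 mg/kg/day, whereas this trial enrols patients under 18 at 20-40 mg/kg/day. The true DFX rate here could be 65% or more. This stands, and it means the limit applies to Table 6's figures and not to the trial's eventual result. It does not rescue the sentence in section 11.1: a rate justified on those grounds is not pooled from Table 6, and the plan offers no such justification.

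It can also be said that both sections already call the rates assumptions, so the 80% is already conditional. That is fair. What remains open is the source given for the assumption.

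A reader might go further and infer that the trial is underpowered or should enrol more patients. The documents do not support this. Power depends on the DFP rate as well as the DFX rate, and Table 6 favours DFP on ferritin. With both arms taken from the table and equal dependence, power is about 97% or more. The opposite inference, that power is safely high, is not supported either: it rests on a cross-study comparison and on equal A-B dependence, which nothing in the plan establishes.

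**Conclusion.** The stated derivation is wrong as written. Under the endpoint rule, Table 6 allows a DFX composite of at most 57% (63.3% at the upper confidence limit), not 65%. Put the other way, 65% implies a DFX ferritin success rate of at least 65%, even if every scanned patient also meets criterion B. The limit assumes that Table 6's ferritin rate is the criterion A rate in the trial population; it needs no assumption about scanned share, T2* rate or dependence.

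The fault lies in the source of a sample-size input. The arithmetic from 65% v 67.5% to 310 patients is right, and the primary analysis uses observed proportions and is unaffected. The effect on power cannot be fixed from the documents: it ranges from about 60% (57% in both arms) to above 99% (Table 6 in both arms, equal dependence, 60-70% scanned). It should be corrected, since it concerns the primary sample size and the correction is cheap.

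**What to change.** In section 11.1, replace the pooling sentence in one of two ways.

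1. Derive both rates by the endpoint rule, p = (1 − f) × pA + f × P(A and B). State the assumed share f with evaluable cardiac T2* and the assumed dependence between A and B, vary both, and note that 69.5% applies only to baseline T2* of 10 to <20 ms.
2. Keep 65% and 67.5% as planning assumptions, justify them under criterion A, state the implied DFX ferritin rate of at least 65%, and remove the attribution to Table 6.

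In section 11.12, report the power of 310 evaluable patients over a range of inputs in place of the single 80%: 79.8% at 65% v 67.5%; 76.4% at 57% v 59.5%; 60.4% at 57% v 57%. For Table 6 point estimates in both arms, give about 97% or more only on condition of equal, non-negative A-B dependence, and show alongside it the fall to about 67% at 70% scanned with DFX at maximum overlap and DFP independent.

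The cost is wording and a short power table. The margin and the analysis stay as they are, and this point does not call for more patients. The plan gives up a single headline power figure.

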11.2 Study population

Intent to treat population

For the intent to treat (ITT) analysis all patients that have been randomized and start therapy will be included.

Per protocol population

Patients in the per protocol (PP) population for the primary efficacy analysis (PP1) are those that have received the study drugs and for whom the composite endpoint is available at baseline and after 1 year treatment, without major protocol violations.

For the secondary efficacy evaluation assessed as non-inferiority of DFP to DFX in terms of serum ferritin levels the PP population (PP2) includes only patients for whom the measure of serum ferritin is available at baseline and after 1 year treatment.

For the secondary efficacy evaluation assessed as non-inferiority of DPF to DFX in terms of successfully chelated patients according to cardiac MRI T2* the PP population (PP3) includes only patients for whom the measure cardiac MRI T2* is available at baseline and after 1 year treatment.

Safety population

The population for the safety and tolerability analysis will include all patients having received at least one dose of study medication.

PK and PKPD population

The population for the pharmacokinetic and subsequent exploratory analyses (e.g. correlation between systemic exposure and ferritin levels) will include patients who have received the investigational drugs throughout the duration of the study (i.e., 1 year) and have had a blood sample collected for the assessment of drug concentrations in plasma.

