4. STUDY DESIGN

This is a Phase III study, providing efficacy and safety data after one year treatment with DFP and DFX.

No studies directly comparing DFP and DFX are available. Published literature including the most recent meta-analyses (Roberts D et al, 2007; Maggio A et al, 2010; Meerpohl JJ et al, 2012) compares the efficacy of both IMPs with that of DFO and demonstrate that their efficacy profiles are non inferior to those of DFO. These findings refer mainly to adults but include also some data in the paediatric population. On this basis testing for non-inferiority of DFP versus DFX is well supported.

Thus, this study has been designed as a multicentre, randomized, open label, active comparator controlled, parallel group trial for establishing the non-inferiority of DPF to DFX in terms of changes in ferritin levels and cardiac iron concentration in paediatric patients after 1 year of treatment.

Evidence that serum ferritin is a reliable parameter to evaluate any chelator efficacy has been widely published (Gabutti V and Piga A. 1996; Olivieri, N. et al 1994; Telfer PT, 2000; Borgna-Pignatti, 2004) and represents the basis for monitoring therapy and assessing efficacy particularly in the paediatric population.

However, more recent literature highlights also the important role of cardiac MRI T2* in the understanding and treatment of cardiac siderosis. In the paediatric population iron accumulation in the heart begins to be evident later than in the liver and evidence has been accumulating suggesting that the use of MRI T2* is not of value in chelated patients prior to about 10 years of blood transfusions (Wood JC, 2008, Meloni A., HTA-Thal project funded by Italian Ministry of Health, final project meeting, Rome, June 28, 2011; Guidelines for the clinical management of Thalassaemia, 2nd revised edition, Thalassaemia International Federation, 2008). Moreover, cardiac MRI T2* evaluation has limited application to younger patients unable to undergo the scan without being sedated. For the above mentioned reasons, the performance of a cardiac T2* in children over 10 years is generally recommended in clinical practice, unless clinical condition suggests a cardiac evaluation before that age.

On such evidence, treatment efficacy will be measured in terms of percentage of successfully chelated patients assessed with ferritin and cardiac MRI T2* as defined in **Section 4.3**.

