6.5 Blinding

Blinding is not foreseen for this trial because of the different pharmaceutical forms and posology of IMPs which would have heavily impacted on the study feasibility.

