11.6 Efficacy evaluation

Primary efficacy

The primary efficacy evaluation will be based on a treatment success rate defined in Section 4.3 Primary endpoint. The primary analysis will be based on the PP1 population.

In addition, an ITT analysis will be performed to corroborate the findings. If no composite endpoint is estimable at 1 year treatment (unavailability of serum ferritin and/or MRI determination either at baseline or after 1 year treatment), the subject is considered a treatment failure in the ITT analysis. Non-inferiority will be assessed based on the two sided 95% confidence interval $[\delta_L, \delta_U]$ of the difference $\delta = p_1 - p_2$, being p_1 and p_2 the proportion of success in the n_1 and n_2 patients randomised to DFP and DFX arms, respectively. Non-inferiority will be claimed if δ_L is greater than -0.125. The two sided 95% confidence interval for δ will be estimated based on asymptotic normal approximation for the difference of two binomial probabilities as follows:

$$(p_1 - p_2) \pm Z_{1-\alpha/2} \sqrt{Var(p_1 - p_2)}$$

where Z_γ is the γ^{th} percentile of the standardised normal distribution and

$$Var(p_1 - p_2) = p_1(1 - p_1)/n_1 + p_2(1 - p_2)/n_2$$

If non-inferiority of DFP to DFX is established based on the PP1 population and the confidence interval for the null hypothesis of non-inferiority based on the ITT population is similar or the percentage of success for DFP is greater than that of DFX in magnitude, the hypothesis that DFP is superior to DFX in terms of the defined success criteria will be tested at the one-sided alpha level of 0.025. Superiority testing will be based on the ITT population. The rationale for superiority is justified by the known beneficial effects of DFP at the cardiac level.

Secondary efficacy

Efficacy measured through serum ferritin levels

Serum ferritin will be analysed as secondary measure of treatment efficacy. Serum ferritin is a well validated and clinically widespread surrogate measure of iron load, highly correlated with iron in the liver. It represents an easy to assess parameter in the paediatric population.

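### The set labelled ITT leaves out randomised patients who never start therapy, which conflicts with the randomised denominators in Section 11.6 and could bias the open-label superiority test.

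*Combined protocol and SAP*

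**What the plan says.** All references are to the combined protocol and SAP.

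- **ITT set (11.2).** For the ITT analysis, "all patients that have been randomized and start therapy will be included". Two conditions apply: randomised, and therapy started.
- **Denominators (11.6).** The success proportions and their confidence interval use n1 and n2, described as the "patients randomised to DFP and DFX arms, respectively". Starting therapy is not mentioned. The ferritin comparison in the same section also takes n1 and n2 as numbers randomised.
- **Missing endpoint (11.6).** If the composite cannot be determined at one year, "the subject is considered a treatment failure in the ITT analysis".
- **Use of the sets (11.6).** For non-inferiority, "The primary analysis will be based on the PP1 population", with an ITT analysis in support. If the conditions for going on are met, "Superiority testing will be based on the ITT population". ITT also supports the ferritin non-inferiority comparison and is the set for the ferritin trend analysis.
- **Masking (4 and 6.5).** The design is a "multicentre, randomized, open label, active comparator controlled, parallel group trial", and "Blinding is not foreseen for this trial because of the different pharmaceutical forms and posology of IMPs".
- **Timing (7.2.1).** Randomisation, dispensing and the start of treatment all fall on Day 0.

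**The concern.** An ITT analysis keeps every randomised patient in the arm assigned, so that nothing that happens after allocation decides who is compared. The Section 11.2 set lets one post-allocation event, not starting therapy, remove a patient.

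In a blinded trial one could argue that this event cannot depend on the arm. That argument is not available here. Families know the allocation, and the regimens differ: DFP is an oral solution three times a day (6.1), and DFX is a tablet dispersion once a day on an empty stomach (6.2). Section 11.13 itself allows that compliance might be better with once-daily DFX. Patients already taking DFX or DFP are eligible (5.1), so some will be allocated away from their current oral drug.

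The analyses at stake are the superiority test, the ITT analysis that corroborates non-inferiority, and the ITT ferritin analyses. Separately, an analyst with a randomised non-starter in hand finds one section that excludes the patient and another that counts the patient in the denominator.

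**Working it through.** **1. Does any rule bring non-starters back?**

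| Place | What it covers | Restores a non-starter? |
|---|---|---|
| 11.2, ITT | randomised and started | No, excludes |
| 11.6, failure rule | missing endpoint within the ITT analysis | Not clearly; it acts on patients already in the set |
| 11.6, n1 and n2 | patients randomised to each arm | Implies yes, against 11.2 |
| 9 and 11.13 | withdrawal from treatment or early discontinuation counts as failure | Not stated; says nothing on set membership |

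So there is an explicit exclusion, a conflicting denominator, and no rule that settles the matter.

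**2. The plan's own figure.** Inputs from 11.12: DFX 65%, DFP 67.5%, one-sided alpha 0.025, power 80%. The margin of 12.5 points is in 4.1.

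n per arm = (0.65×0.35 + 0.675×0.325) × (1.960 + 0.842)² / (0.025 + 0.125)² ≈ 155.9, so 156 per arm or 312 in total, against 310 stated. Power at 155 per arm is 79.8%. Inflation: 310/0.80 = 387.5, so 388, or 194 per arm. The sample size reproduces and does not depend on the ITT definition.

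**3. Superiority test.** Assumptions, none from the documents except the 65% (taken from the DFX planning rate): all-randomised success is 65% in both arms, with non-starters counted as failures; k DFP patients and no DFX patients fail to start.

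The Section 11.2 set then has n1 = 194 − k and p1 = 0.65×194/(194 − k) = 126.1/(194 − k). With the variance formula of 11.6, SE = √[p1(1 − p1)/n1 + 0.65×0.35/194], and the chance that the test succeeds is 1 − Φ(1.960 − (p1 − 0.65)/SE).

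| k | n1 | p1 | Shift (points) | SE | Chance of superiority |
|---|---|---|---|---|---|
| 0 | 194 | 65.0% | 0 | 0.0484 | 2.5% |
| 4 | 190 | 66.4% | 1.4 | 0.0485 | 4.7% |
| 6 | 188 | 67.1% | 2.1 | 0.0484 | 6.3% |
| 10 | 184 | 68.5% | 3.5 | 0.0484 | 10.9% |

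These are for the test taken alone. The gate in 11.6 (non-inferiority first) can only lower them.

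**4. Corroborating ITT non-inferiority analysis.** Assume starters succeed at 67.5% (DFP) and 65% (DFX). The Section 11.2 set then shows +2.5 points whatever the number of non-starters. With all 194 per arm and non-starters as failures:

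| Non-starters DFP / DFX | DFP rate | DFX rate | Difference | 95% lower limit |
|---|---|---|---|---|
| 0 / 0 | 67.5% | 65.0% | +2.5 | −6.9 |
| 4 / 0 | 0.675×190/194 = 66.1% | 65.0% | +1.1 | −8.4 |
| 10 / 0 | 0.675×184/194 = 64.0% | 65.0% | −1.0 | −10.5 |
| 20 / 0 | 0.675×174/194 = 60.5% | 65.0% | −4.5 | −14.1 |
| 10 / 10 | 64.0% | 0.65×184/194 = 61.6% | +2.4 | −7.2 |
| 0 / 10 | 67.5% | 61.6% | +5.9 | −3.7 |

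Equal loss changes almost nothing. Loss in DFX alone means the current set understates DFP. In these cases the lower limit passes −12.5 only at 20 one-sided non-starters, about 10% of the arm.

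**The case against.** The strongest reply is that the case will hardly arise. Families are informed and consent at Visit 1, and patients on a chelator go through washout. Randomisation comes at the end of the Day 0 visit, when the drug is dispensed and must be started. A family unwilling to accept either regimen has several earlier points at which to leave. Nothing in the documents suggests 4 to 10 refusals in one arm and none in the other. This stands: it limits the likely size, but does not close the window.

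A second reply is that Section 11.6 already uses randomised denominators and counts missing endpoints as failures, and that Section 11.13 can be read to cover a refusal after allocation. That is a fair reading of those sections, but it contradicts Section 11.2 and does not override it. It shows a conflict to be settled, not a plan that is already clear.

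A third is that the error rates above depend on the estimand. They set equality on the all-randomised scale, so under the assumption DFP starters really do better than 65%. That also stands. The rates describe a claim about all randomised patients, which is what the ITT label promises.

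A reader might go further and infer that the randomised comparison is broken, or that the non-inferiority conclusion is at risk. The documents do not support this. The primary decision rests on PP1, which requires receipt of study drug and an endpoint at one year, so non-starters are outside it under any ITT definition. Nor is the 12.5-point margin the right yardstick for superiority, which has no margin.

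**Conclusion.** The point holds as a definitional conflict with a possible, probably small, bias. Section 11.2 describes a modified ITT under the ITT label, and Section 11.6 uses denominators that do not match it. Bias in the superiority test, the corroborating ITT analysis or the ITT ferritin analyses needs non-starters to occur and to differ between arms; its direction is not fixed.

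Under assumed DFP-only loss of 4, 6 or 10 of 194 and 65% all-randomised success in both arms, the superiority test succeeds with probability of about 4.7%, 6.3% or 10.9% instead of 2.5%. These are scenarios, not predictions, because the documents give no non-starter rate. The primary PP1 decision and the sample size of 388 are unchanged. This is a cheap improvement rather than a serious fault.

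**What to change.** 1. In Section 11.2, define ITT as all randomised patients, analysed in the arm allocated.
2. State that a randomised patient who never starts counts as a failure for the binary endpoint, under the existing missing-endpoint rule of Section 11.6.
3. Make Section 11.2 agree with the n1 and n2 definitions in Section 11.6, for both the success rates and ferritin. The failure rule does not carry over to ferritin as a continuous measure, so say how non-starters enter those ITT analyses.
4. Report the number of non-starters and their reasons by arm.
5. Keep the started-therapy set as a supportive analysis, labelled modified ITT.

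The cost is wording only: no extra patients, visits or measurements. The downside is that counting non-starters as failures slightly lowers the success rates; for example, 4 non-starters take a 67.5% rate to 66.1%.
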